# 9.6.3 Exploratory endpoints

Exploratory efficacy endpoints are:

- Overall survival: defined as the time from first study treatment administration to death from any cause. Patients without death prior to the analysis cut-off date will be censored at the last date the patient was known to be alive or the cut-off date, whichever comes first.
- Time to response: defined as the time from first study treatment administration to the first response (PR or CR in radiographic objective response, or PSA decline ≥50% for patients with mCRPC) that is subsequently confirmed (RECIST 1.1 for patients with NSCLC and PCWG3 criteria for patients with mCRPC).

For patients with NSCLC, exploratory efficacy endpoint also includes:

• ORR by iRECIST (Appendix B) for patients with NSCLC.

For patients with mCRPC (to be assessed per PCWG3 criteria), exploratory efficacy endpoints also include:

- PSA RR: PSA response is defined as a PSA decline of ≥50% from baseline that is subsequently confirmed.
- Radiographic RR: radiographic response is defined as radiographic objective response assessed and confirmed by investigator.
- Duration of PSA response: defined as the time from the date of the PSA first decline of ≥50% from baseline that is subsequently confirmed to the date of first confirmed PSA progression or death, whichever occurs first. PSA progression for patients who have achieved a ≥50% decrease from baseline is defined as at least a 25% increase and an absolute increase of ≥2 ng/mL above the nadir (the lowest PSA value on study). The same censoring rules as for DOR will be used.
- Duration of radiographic response: defined as the time from the date of the first radiographic response (PR or CR) that is subsequently confirmed to the date of first radiographic progression or death, whichever occurs first. The same censoring rules as for DOR will be used.
- Time to PSA response: defined as the time from first study treatment administration to the first PSA response that is subsequently confirmed.
- Time to radiographic response: defined as the time from first study treatment administration to the first radiograph response that is subsequently confirmed.

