- Time to PSA progression: defined as the time from first study treatment administration to the date of first confirmed PSA progression. For patients who have achieved a ≥50% decrease from baseline, PSA progression is defined as at least a 25% increase and an absolute increase of ≥2 ng/mL above the nadir (the lowest PSA value on study). For patients without a PSA decrease of this magnitude or no decrease at all, PSA progression is defined as at least a 25% increase and an absolute increase of ≥2 ng/mL above the baseline. Death from prostate cancer or any other cause without prior evidence of PSA progression will not count as an event. If no event exists, then time to PSA progression will be censored at the last scheduled PSA assessment on study or date of death, whichever occurs first.
- To explore the relationship between clinical response and CD38 expression (in infiltrating immune cells and tumor cells), PD-L1 expression (in tumor cells) and immune contexture in tumor at baseline as potential predictive markers of response.
- To explore tumor and immune genetic markers at baseline: tumor mutational load and MSI status in tumor as well as tumor mutational profile and immune genetic determinants in blood.
- To evaluate pharmacodynamic biomarkers in response to IMP: immunophenotype in peripheral blood, immune contexture in tumor and plasma or serum cytokine levels.
- A panel of tumor somatic mutations (ie, tumor mutational profile) will be analyzed at baseline and upon treatment in plasma cell free DNA from peripheral blood.
- Determination of exposure-response relationships with efficacy, safety, and biomarkers, if possible.

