#### Disease assessment

- Tumor imaging: CT or MRI scan every 9 weeks starting at the end of Cycle 3 ( $63 \pm 7$  days) and whenever disease progression is suspected (the same method of assessment should be used throughout the study). Tumor imaging timing should follow calendar days and should not be adjusted for delays in cycle starts.
  - If initial evidence of RECIST 1.1 defined progression is documented, patients could continue treatment while waiting for PD confirmation scan 4 weeks after providing the patients are clinically stable as detailed in Section 6.7.1. When treatment is continued beyond RECIST 1.1 defined tumor progression, subsequent imaging assessments should be based upon iRECIST criteria (Appendix D).
  - For patients with mCRPC, bone lesions are not considered "non-measurable" lesion pre RECIST 1.1. Bone lesions will be assessed by bone scan only.
- Prostate-specific antigen assessment every 9 weeks starting at the end of Cycle 3 (63 ±7 days) for patients with mCRPC. Patients with PSA progression (Appendix A) in the absence of radiographic progression should continue IMP (local laboratory).
- Bone scan for patients with mCRPC, every 9 weeks starting at the end of Cycle 3 (63 ±7 days). In cases of PD based on bone scan only, the bone scan should be repeated after 6 weeks to confirm the progression using the 2+2 rule (2 new lesions on first scan, with at least 2 additional lesions on the confirmatory scan; refer to Appendix A) as detailed in Section 6.7.1. In case of doubtful lesions on bone scan, bone-centered X-ray or MRI scan should be performed to confirm the nature of those lesions (metastatic or not).

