Abbreviations: CNS=central nervous system; CT=computed tomography; MRI=magnetic resonance imaging; PCWG3=Prostate Cancer Clinical Trials Working Group 3; PET=Positron emission tomography; PSA=Prostate-specific antigen; PSADT=PSA doubling time; RECIST=Response Evaluation Criteria in Solid Tumors.

Table 11 - Prostate Cancer Clinical Trials Working Group 3 criteria for progression during study

Variable	Progression criterion	
Blood based		
PSA	Recognize that a favorable effect on PSA may be delayed for ≥12 weeks, even for a cytotoxic drug.	
	Monitor PSA by cycle but plan to continue through early rises for a minimum of 12 weeks unless other evidence of progression.	
	Ignore early rises (before 12 weeks) in determining PSA response.	
	Standards for reporting PSA progression date may not indicate a need to stop treatment. After decline from baseline: record time from start of therapy to first PSA increase that is $\geq$ 25% and $\geq$ 2 ng/mL above the nadir, and which is confirmed by a second value $\geq$ 3 weeks later (ie, a confirmed rising trend); the requirement for an increase of 5 ng/mL was decreased to 2 ng/mL, and the requirement for a 50% increase was reduced to 25%. No decline from baseline: PSA progression $\geq$ 25% increase and $\geq$ 2 ng/mL increase from baseline beyond 12 weeks.	
	Recording the duration of PSA decline of little value.	
Imaging		
Nodal and visceral	General:	
	Record changes in nodal and visceral (lung, liver, adrenal, and CNS) disease separately.	
	Use RECIST 1.1 but clearly record type of progression (growth of existing lesions versus development of new lesions) separately by site.	
	The recommendations apply to both nmCRPC and mCRPC	
	Record up to 5 lesions per site of spread.	
	Report the proportion who have not progressed at fixed time points (6 or 12 months).	
Nodal	Note that for some treatments, a lesion may increase in size before it decreases	

Variable	Progression criterion				
	Previously normal (<1.0 cm) lymph nodes must have grown by $\geq$ 5 mm in the short axis from baseline or nadir and be $\geq$ 1.0 cm in the short axis to be considered to have progressed.				
	Nodes that have progressed to 1.0 to less than 1.5 cm are pathologic, subject to clinical discretion, and nonmeasurable.				
	For existing pathologic adenopathy (≥1.5 cm), progression is defined per RECIST 1.1.				
	Exclude pseudoprogression in the absence of symptoms or other signs of progression.				

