- rPFS by iRECIST: For mCRPC patients, rPFS is defined as the time from first study treatment administration to the date of first documented radiographic progression that is subsequently confirmed or the date of death from any cause, whichever occurs first. The same censoring rule as PFS will be used
- PSA response rate: defined as a PSA decline of $\geq 50\%$ from baseline that is subsequently confirmed
- Radiographic RR: defined as radiographic objective response assessed and confirmed by investigator

- Duration of PSA response: defined as the time from the date of the PSA first decline of $\geq 50\%$ from baseline that is subsequently confirmed to the date of first confirmed PSA progression or death, whichever occurs first. PSA progression for patients who have achieved a $\geq 50\%$ decrease from baseline is defined as at least a 25% increase and an absolute increase of ≥ 2 ng/mL above the nadir (the lowest PSA value on study). The same censoring rules as for DOR will be used
- Duration of radiographic response: defined as the time from the date of the first radiographic response (PR or CR) that is subsequently confirmed to the date of first radiographic progression or death, whichever occurs first. The same censoring rules as for DOR will be used
- Time to PSA response: defined as the time from first study treatment administration to the first PSA response that is subsequently confirmed
- Time to radiographic response: defined as the time from first study treatment administration to the first radiograph response that is subsequently confirmed
- Time to PSA progression: defined as the time from first study treatment administration to the date of first confirmed PSA progression. For patients who have achieved a $\geq 50\%$ decrease from baseline, PSA progression is defined as at least a 25% increase and an absolute increase of ≥ 2 ng/mL above the nadir (the lowest PSA value on study). For patients without a PSA decrease of this magnitude or no decrease at all, PSA progression is defined as at least a 25% increase and an absolute increase of ≥ 2 ng/mL above the baseline. Death from prostate cancer or any other cause without prior evidence of PSA progression will not count as an event. If no event exists, then time to PSA progression will be censored at the last scheduled PSA assessment on study or date of death, whichever occurs first

For patients with NSCLC, the following endpoint will also be summarized:

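### Time to PSA progression uses a rule that differs from the PCWG3 criteria in Appendix A, Table 11, in patients whose PSA falls by less than 50% or not at all

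*SAP*

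**What the plan says.** The lead-in to the prostate endpoints in protocol 9.6.3 reads: "For patients with mCRPC (to be assessed per PCWG3 criteria), exploratory efficacy endpoints also include". Time to PSA progression is one of them. After a fall of at least 50%, progression is a rise of at least 25% and at least 2 ng/mL above the nadir. SAP 2.1.3.3 gives the same rule and continues: "For patients without a PSA decrease of this magnitude or no decrease at all, PSA progression is defined as at least a 25% increase" together with at least 2 ng/mL, both measured from baseline. Progression must be confirmed, but no interval is given. Neither section has a minimum time on treatment.

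Protocol 12.3.2 sends the reader to Appendix A for the same concept: "Patients with PSA progression (Appendix A) in the absence of radiographic progression should continue IMP". Within Appendix A, Table 9 does not define PSA progression and Table 10 concerns trial entry, so the reference can only mean Table 11, the PCWG3 criteria for progression during study. Table 11 has two branches:

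- "After decline from baseline: record time from start of therapy to first PSA increase" of at least 25% and at least "2 ng/mL above the nadir, and which is confirmed by a second value" 3 or more weeks later. There is no 50% condition.
- With no decline, a rise of at least 25% and at least 2 ng/mL, the latter written as an "increase from baseline beyond 12 weeks".

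SAP 1.5 records no modification to the protocol's statistical section, and no other section reconciles the two rules.

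**The concern.** The protocol names one standard and prints it, then defines the endpoint differently. The differences act in opposite directions. A patient with a modest PSA fall must climb back past baseline before counting as progressed, so the event comes late. It may never be recorded: PSA follow-up after treatment continues only if treatment stopped without progression, it is not required after new anticancer therapy, and patients without an event are censored at the last scheduled PSA or at death. A patient whose PSA rises from the start can be counted before the time at which Table 11 begins to count. The Kaplan-Meier analysis planned in SAP 2.4.5.2 would mix both effects, and a reader would take the result for the PCWG3 endpoint.

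**Working it through.** The plan gives no figure to reproduce. The check compares the thresholds and the dates that the two rules produce.

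**Inputs.** The two definitions come from protocol 9.6.3 / SAP 2.1.3.3 and from Appendix A, Table 11. The PSA schedule comes from protocol 9.6.1 and flowchart 1.3: every 9 weeks from day 63 ±7, and at end of treatment if there was none in the past 30 days. The end-of-treatment visit is 30 ±7 days after the last dose (protocol 12.4). Baseline PSA and doubling time are not in the documents and are assumed.

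**Thresholds.** Threshold = max(1.25 × reference, reference + 2 ng/mL). Under 9.6.3/SAP the reference is the nadir if the fall is at least 50%, otherwise baseline. Under Table 11 it is the nadir after any decline, otherwise baseline. With baseline 100 ng/mL (assumed):

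| Nadir | 9.6.3 / SAP | Table 11 | Ratio |
|---|---|---|---|
| 50 | 62.5 | 62.5 | 1.00 |
| 51 | 125 | 63.75 | 1.96 |
| 60 | 125 | 75 | 1.67 |
| 70 | 125 | 87.5 | 1.43 |
| 80 | 125 | 100 | 1.25 |
| 90 | 125 | 112.5 | 1.11 |
| No decline | 125 | 125, only after day 84 | 1.00 |

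The 9.6.3/SAP threshold halves, from 125 to 62.5, as the nadir moves from 51 to 50. So the patient with the slightly smaller fall may rise twice as high before progressing. At a baseline of 10 ng/mL the 2 ng/mL floor narrows the gap: at nadir 5.1 the thresholds are 12.5 and 7.1, a ratio of 1.76.

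**Delay after a partial fall.** With exponential regrowth, delay = log2(ratio) × doubling time. For assumed doubling times of 2, 3 and 6 months:

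- Nadir 90: log2(125/112.5) = 0.152, giving 0.3, 0.5 and 0.9 months.
- Nadir 60: log2(125/75) = 0.737, giving 1.5, 2.2 and 4.4 months.

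PSA is scheduled only every 9 weeks (about 2 months), so the observed delay comes in visit-sized steps and can be zero in an individual patient.

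**No decline.** Twelve weeks is day 84. The first scheduled on-treatment PSA falls on days 56 to 70 (63 ±7), before that limit. The second falls on days 119 to 133 (126 ±7). Under 9.6.3/SAP, a qualifying rise at the first visit is dated there once it is confirmed, taking a confirmed progression to be dated at the first of its two values. Under Table 11 the rise counts only from a PSA after day 84. That is normally the week-18 visit, but an end-of-treatment PSA can come sooner: a last dose at Cycle 4 Day 1, about day 64, puts that visit near day 64 + 30 = 94.

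**The case against.** The strongest reply is that the analyst faces no ambiguity. Protocol 9.6.3 and the SAP give the same explicit rule, and Table 11 is reproduced guideline material that the study departs from elsewhere. For instance, Table 11 asks for PSA by cycle and sees little value in the duration of PSA decline, while the study measures every 9 weeks and makes duration of PSA response an endpoint. The first part stands: the SAP can be programmed as it is written. But protocol Section 17 makes the appendices part of the protocol, 9.6.3 claims PCWG3, and 12.3.2 relies on Appendix A for this very concept. The departure is undeclared.

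Several stronger readings are tempting and not supported:

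- A reader might infer that a week-9 rise alone is an event. It is not; both documents require confirmation.
- Table 11's advice to disregard rises before 12 weeks might be taken to cover progression. That sentence concerns PSA response. For progression, the 12-week condition belongs only to the no-decline branch.
- The SAP might be thought to label the endpoint PCWG3. Its bullet and lead-in do not; the label is in the protocol.
- The result might be called incomparable with other trials. That depends on definitions used in trials outside these documents. The supportable statement is that it should not be reported as the PCWG3 endpoint.

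**Conclusion.** The conflict is real and limited. For PSA falls short of 50%, the plan's threshold is 1.11 to 1.96 times Table 11's for nadirs from 90% down to 51% of an assumed baseline of 100 ng/mL, which delays or censors events. For patients without a decline, a confirmed rise can be dated at about week 9 instead of at a PSA after day 84. The delays in months are illustrations under assumed doubling times. The documents do not show how many patients fall in each group, so neither the size nor the direction of the net effect on the curve can be stated.

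A reader might also infer damage to the main efficacy results. The documents do not support that. PSA progression does not enter response rate, PFS or DOR, and on its own it does not stop treatment. Duration of PSA response already uses the nadir, as Table 11 does, and shares only the unstated confirmation interval. The threshold and 12-week differences affect one exploratory endpoint, time to PSA progression, in a non-comparative study. This is a minor point, worth correcting because the correction is cheap.

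**What to change.** Align protocol 9.6.3 and SAP 2.1.3.3 with Table 11:

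- after any decline, a rise of at least 25% and at least 2 ng/mL above the nadir, confirmed at least 3 weeks later;
- with no decline, a rise of at least 25% and at least 2 ng/mL above baseline, beyond 12 weeks, keeping the existing requirement that progression be confirmed. Table 11 attaches its 3-week interval only to the first branch, so copying it literally would drop confirmation here.

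If the present rule is kept, say in SAP 2.1.3.3 that it departs from PCWG3 and why, do not label the result PCWG3, and add the Table 11 version as a sensitivity analysis.

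Both routes use the PSA data already planned. The second needs only SAP wording and derivation code. The first also changes protocol text, which means an amendment with ethics committee review under protocol Section 17.

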2.1.4 Safety endpoints

The safety analysis will be based on the reported adverse events (AEs) and other safety information, such as clinical laboratory data, vital signs, weight, electrocardiogram (ECG) and Eastern Cooperative Oncology Group (ECOG) performance status.

Observation period

The observation period starts from the time when the patient gives informed consent and is divided into 3 periods:

- **The pre-treatment period** is defined as the time informed consent is signed until the first dose of study treatments administration

- The **treatment-emergent adverse event (TEAE) period** is defined as the time from the first dose of study treatments up to 30 days after last dose of study treatments
- The **post-treatment** period is defined as the time starting from 31 days after the last dose of study treatments to the end of the study (as defined in the protocol)

2.1.4.1 Dose limiting toxicities (DLTs)

For the phase 1 part dose limiting toxicities will be listed by patient using the DLT evaluable population.

2.1.4.2 Adverse events variables

AEs (including serious adverse events [SAEs] and AEs of special interest [AESIs]) will be collected from the time of signed informed consent until the end of study.

Adverse event observation period

- **Pre-treatment AEs** are defined as any adverse event reported during the pre-treatment period
- **TEAEs** are adverse events that developed or worsened or became serious during the TEAE period
- **Post-treatment AEs** are adverse events that developed or worsened or became serious during the post-treatment period

All AEs (including SAEs and AESIs) will be graded according to NCI-CTCAE v4.03 and coded to a lower-level term, preferred term (PT), high-level term, high-level group term and associated primary system organ class (SOC) using the version of MedDRA currently in effect at Sanofi at the time of database lock.

Adverse events of special interest

Specific analyses will be performed for the following AEs:

- **DLTs**
- **Grade ≥ 2 IARs.** An IAR occurs typically within 24 hours from the start of the infusion
- **Grade ≥ 3 immune-related TEAEs**
- **Immune-related AEs of any grade in a patient previously treated with a PI3K inhibitor (only applicable for patients who receive REGN2810)**
- **Pregnancy** of a female patient entered in a study as well as pregnancy occurring in a female partner of a male patient entered in a study with IMP/non-investigational medicinal product (NIMP)
- **Symptomatic overdose** (serious or non-serious) with IMP/NIMP

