- aa PSA assessment: For patients with mCRPC, to be performed at baseline (within 14 days before initiation of IMP). Repeat at Cycle 1 Day 1, every 9 weeks starting at the end of Cycle 3 (63 ±7 days; disease assessment timing should follow calendar days and should not be adjusted for delays in cycle start), at the EOT visit (if not performed in the past 30 days) and during follow-up (if discontinue IMP without PD, repeat every 90 days). PSA responses are to be confirmed no less than 4 weeks later. PSA assessment is not needed for patients who start another anti-cancer treatment regimen.
- bb Bone scan: Mandatory for patients with mCRPC (diagnostic quality scans performed as part of routine clinical management within 6 weeks prior to IMP initiation are acceptable). Repeat every 9 weeks at the end of Cycle 3 (63 ±7 days; disease assessment timing should follow calendar days and should not be adjusted for delays in cycle start), at the EOT visit (if not performed in the past 30 days) and during follow-up (if discontinue IMP without PD, repeat every 90 days). If progression is defined by bone scan only, the bone scan should be repeated no less than 6 weeks to confirm the progression, see Section 6.7.1. In case of doubtful lesions on bone scan, bone-centered X-ray or MRI scan should be performed to confirm the nature of those lesions (metastatic or not). Study sites must retain disease assessment images, as Sponsor may decide to collect these images for possible Independent Central Review in the future.
- cc REGN2810/Isatuximab Administration: At the start of each treatment cycle, the patient's weight will be determined. REGN2810 administration is only applicable in cohorts receiving isatuximab in combination with REGN2810.

Amended Clinical Trial Protocol No. 05 SAR650984-ACT15319 - isatuximab 11-Jun-2019 Version number: 1

dd AE/SAE assessment: All AEs, including adverse events of new onset as well as worsening of baseline signs and symptoms are to be reported from the signing of the informed consent to 30 days following the last administration of study treatment. After the 30 day all ongoing related non-serious AEs, ongoing SAE and new related AE/SAEs are to be followed to resolution or stabilization. Stabilization is defined as an AE ongoing without any change for at least 3 months. Severity will be graded according to NCI-CTCAE version 4.03.

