#### 9.1.2 Adverse events

Adverse events will be collected from the signing of the study informed consent form to 30 days after the last IMP administration. Beyond 30 days after last IMP administration all ongoing non-serious AEs, ongoing SAEs and new treatment-related AEs/SAEs are to be followed to resolution or stabilization. Adverse events encountered before the start of isatuximab and REGN2810 treatment or later than 30 days after the last IMP administration will be summarized separately.

All AEs will be graded according to the NCI-CTCAE version 4.03, and will be coded to a "Preferred Term" (PT) and associated primary "System Organ Class" (SOC) using the Medical Dictionary for Regulatory Activities (MedDRA). Adverse events will be summarized and analysed with respect to the type, frequency, severity, seriousness, relatedness, and outcome.

The general and study-specific safety criteria are presented in Section 10.

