#### 12.5.3 Post overall survival study cut-off date

Patients still on study treatment after the study cut-off date (12 months after last patient initiates IMP) can continue study treatment until at least 1 treatment discontinuation criterion as defined in Section 6.7 is met. The following information will be collected during the study treatment administration:

- IMP administration.
- Disease assessment (for patients who are still on study treatment, until confirmation of PD, or start with another anti-cancer therapy, or treatment period ended, whichever comes first)
- All SAEs regardless of relationship to study treatment and AEs considered related to study treatment.
- End of treatment reason.

One ADA sample should be drawn 90 days after last study treatment administration. If ADA is positive or inconclusive at 90 days, the repeat samples will be taken every 3 months days until the results become negative (see Section 1.5).

No follow-up information will be collected after these patients discontinue study treatment except all SAEs still ongoing at the end of study treatment and all AEs considered as related to study treatment still ongoing or occurring after the end of study treatment, which will be followed until resolution/stabilization.

11-Jun-2019 Version number: 1

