1.5 MODIFICATIONS TO THE STATISTICAL SECTION OF THE PROTOCOL

Not applicable.

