The number (%) of patients experiencing TEAEs by primary SOC and PT will be summarized by grade (all grades and Grade ≥ 3). Similar tables will be presented for treatment-related TEAEs, serious TEAEs, and TEAEs leading to definitive/premature discontinuation.

TEAEs with an incidence $\geq 5\%$ will be summarized by PT for all grades and Grade ≥ 3 .

Listings of serious TEAEs, TEAEs leading to definitive or premature treatment discontinuation will be provided.

Infusion associated reactions (IARs)

IAR analysis will include all adverse events regardless of relationship to isatuximab, cemiplimab or NIMP. The IARs will be summarized as follow:

- Number (%) of patients experiencing IARs according to investigator reported AEs presented by primary SOC and PT will be summarized by grade,
- Description of the IAR diagnoses (using the diagnosis reported and excluding symptoms)
 - Number (%) of patients action taken
 - Number (%) of patients with only 1, ≥ 1 , ≥ 2 , ≥ 3 , ≥ 4 and ≥ 5 episodes
 - Number (%) of patients with first occurrence of IAR at the first infusion and subsequent infusions
 - Number (%) of patients with IAR at the first and subsequent infusions
 - Number (%) of patients with at least two episodes of IARs at the same infusion
 - Day of onset from infusion
 - Duration (in days)
- Number of patients with symptoms of IARs (as reported by investigator) by SOC and PT

Analysis of adverse events of special interest

A listing of patients with at least one AESI described in [Section 2.1.4.2](#) will be provided.

Analysis of pre-treatment and post-treatment adverse events

The following analysis will be provided by grade (all grades and Grade ≥ 3).

- All pre-treatment AEs by primary SOC and PT, showing the number (%) of patients with at least 1 pre-treatment AE, sorted by the internationally agreed SOC order and decreasing incidence of PTs within each SOC
- All post-treatment AEs by primary SOC and PT, showing the number (%) of patients with at least 1 post-treatment AE, sorted by the internationally agreed SOC order and decreasing incidence of PTs within each SOC

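### The SAP treats adverse event collection as unrestricted to end of study, but the protocol stops recording new unrelated events 30 days after last dose, so the table of all post-treatment AEs understates all-cause late incidence

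*SAP*

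**What the plan says.** **SAP.** Section 2.1.4.2 states that AEs, including SAEs and AESIs, "will be collected from the time of signed informed consent until the end of study". The same section says post-treatment AEs "are adverse events that developed or worsened or became serious during the post-treatment period", and section 2.1.4 runs that period from day 31 after last dose to the end of the study. Neither definition refers to relationship to treatment. Section 2.4.6.2 plans the output: "All post-treatment AEs by primary SOC and PT, showing the number (%) of patients with at least 1 post-treatment AE", for all grades and for Grade 3 or higher. Section 1.5, headed "MODIFICATIONS TO THE STATISTICAL SECTION OF THE PROTOCOL", is marked not applicable, so no departure from the protocol is declared.

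**Protocol.** Footnote dd of the section 1.3 flowchart has all AEs reported "from the signing of the informed consent to 30 days following the last administration of study treatment". Section 9.1.2 agrees: "Adverse events will be collected from the signing of the study informed consent form to 30 days after the last IMP administration". Section 10.5.1 makes explicit that recording regardless of seriousness or relationship runs only to that 30-day limit. Beyond it, footnote dd and section 12.5.1 (the day 60 and day 90 visits) keep ongoing related non-serious AEs, ongoing SAEs and new related AEs and SAEs.

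**After the study cut-off.** For patients still on treatment, protocol section 12.5.3 lists the safety data to be collected as "All SAEs regardless of relationship to study treatment and AEs considered related to study treatment".

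**The concern.** The two documents describe different data. The SAP sentence sets one unrestricted window, and the table title says all. The protocol applies a causality filter to new events from day 31. A reader of the table would take its percentages as all-cause incidence of late events, when new unrelated AEs and SAEs were not to be collected.

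The table is likely to be read closely. Protocol section 4.3.2 gives a re-estimated isatuximab half-life of 28 days, so day 31 is about 31/28 = 1.1 half-lives after last dose. Section 4.3.1 says isatuximab had not been tested in solid tumors. Late events will therefore be examined for delayed toxicity. In an open-label study, what reaches the table after day 30 depends on the investigator's view of causality.

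**Working it through.** The plan states no figure on this point, so there is nothing to reproduce. The check compares the collection rules.

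| Period | Protocol collects | SAP assumes |
|---|---|---|
| Consent to last dose + 30 days | All AEs, any cause (1.3 footnote dd, 9.1.2, 10.5.1) | Same |
| From day 31 after last dose | New related AEs/SAEs; follow-up of ongoing events (1.3 footnote dd, 12.5.1) | AEs with no restriction, to end of study (2.1.4.2) |
| On treatment after study cut-off | SAEs of any cause and related AEs (12.5.3) | No separate rule; the treatment-emergent period runs to last dose + 30 days (2.1.4) |

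**Step 1: what can enter the post-treatment table.** New related AEs and SAEs can. So can ongoing events under follow-up that worsen or become serious, because SAP 2.1.4.2 counts these. New unrelated AEs and new unrelated SAEs cannot.

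**Step 2: direction.** A patient whose only late event is new and unrelated stays in the denominator and is absent from the numerator. The reported proportion can therefore only be at or below the true all-cause proportion.

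**Step 3: size.** The documents give neither a late event rate nor the share of late events assessed as related. As an illustration only, assume that new late AEs per patient are Poisson with mean m, and that a share q, independent across events, is assessed as related. Then:

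- true proportion with at least one new late AE = 1 − exp(−m)
- recordable proportion = 1 − exp(−mq)

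| m (assumed) | True | q = 0.10 | q = 0.25 | q = 0.50 |
|---|---|---|---|---|
| 0.25 | 22.1% | 2.5% | 6.1% | 11.8% |
| 0.50 | 39.3% | 4.9% | 11.8% | 22.1% |
| 1.00 | 63.2% | 9.5% | 22.1% | 39.3% |

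The ratio of recordable to true runs from 0.11 (m = 0.25, q = 0.10) to 0.62 (m = 1.00, q = 0.50). It covers new onsets only. Worsening of followed events would add to the table and is not modelled.

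**Step 4: consistency within the protocol.** Two sets of passages disagree.

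- Section 9.1.2 follows all ongoing non-serious AEs beyond day 30. Footnote dd and section 12.5.1 follow only the related ones.
- Section 12.5.3 narrows collection for patients on treatment after the cut-off. Sections 6.7.1, 12.1 and 12.5.2 say these patients continue planned study procedures except PK and ADA. Read alone, that would keep full AE assessment.

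**The case against.** The best defence is that this is loose wording. SAP 2.1.4.2 does not itself say all AEs, and some AEs are collected to the end of study. SAP 2.1.4 bases the safety analysis on reported AEs. The protocol foresees the table: section 9.1.2 has events later than 30 days summarized separately, and section 13.4.5.2 plans tables for the post-treatment period. Treatment-emergent events are the stated primary focus.

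Most of that is right, but it does not remove the problem. The SAP sentence carries no restriction, the table title does say all, and neither document says the table holds a filtered set of events.

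Three stronger readings are tempting, and the documents do not support them.

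- **All-cause coverage ends completely at day 30.** It does not. Ongoing SAEs of any cause are followed, section 9.1.2 extends this to all ongoing non-serious AEs, and either can be counted if they worsen. Deaths after the treatment-emergent period are summarized whatever the cause (SAP 2.1.4.4 and 2.4.6.3).
- **Comparisons between periods are distorted.** No such comparison is planned. SAP 2.4.6.2 describes pre-treatment and post-treatment events separately.
- **A large, calculable part of the treatment-emergent tables is affected after the cut-off.** Neither document says post-cut-off data enter those tables, and protocol section 6.7.2 sets the end of trial at the cut-off. Any share worked out from the two-year treatment limit would measure treatment time under an assumed accrual pattern, not missing AEs.

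**Conclusion.** The point holds in a limited form. SAP 2.1.4.2 states a collection window that the protocol contradicts, and the planned table of all post-treatment AEs will understate all-cause late incidence because new unrelated AEs and SAEs are not collected after day 30. The direction follows from the text alone. The size cannot be derived from the documents; the range of 0.11 to 0.62 rests wholly on the assumed m and q.

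Treatment-related late rates are not lowered by this rule. All-cause deaths, treatment-emergent tables before the cut-off, DLT assessment and the primary response endpoint are untouched. The consequence is one mislabelled safety table, worth correcting because the correction is cheap.

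The post-cut-off question is secondary. It is a conflict between protocol passages that must be reconciled, and the documents do not establish that it biases a planned table.

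**What to change.** 1. Rewrite SAP 2.1.4.2 to give the protocol windows: all AEs from consent to 30 days after last dose, then new treatment-related AEs/SAEs and follow-up of ongoing events.
2. Replace the table of all post-treatment AEs by one titled and defined as new treatment-related AEs/SAEs with onset more than 30 days after last dose. Show worsening of followed ongoing events separately. Add a footnote that new unrelated events were not collected in this period.
3. Reconcile protocol section 9.1.2 with section 1.3 footnote dd and section 12.5.1 on ongoing non-serious AEs, and section 12.5.3 with sections 6.7.1, 12.1 and 12.5.2 on collection after the cut-off.
4. If section 12.5.3 stands, state in the SAP a safety data cut-off for the all-cause treatment-emergent tables, and list later SAEs and related AEs separately.

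The cost is SAP wording, table titles and a footnote, plus a protocol clarification for item 3. Items 1 and 2 need no new data.
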